#### 3.2 Study Outcome Measures

##### 3.2.1 Primary

The primary outcome is the incidence of TMD pain within a 6-month follow-up period (binary dependent variable). TMD pain is deemed to have occurred if the patient's self report in the *Patient 1-, 3- and 6-month Follow-up Questionnaires* endorses either or both of the following questions: Pain in jaw with wide opening, or pain in temples, jaw joints or jaw muscles. The primary analysis will include all available follow-up measures (1, 3, and 6 months) for each patient to estimate the incidence of TMD pain.

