Patient-reported data will be collected via tablets, smart-phones, or computers at baseline during in-office visit(s) with the surgeons. To assist with in-office data collection, participating OMS will be offered tablets. OMS, dental assistants, and patients will provide baseline and follow-up data directly into the electronic data capture (EDC) system that is maintained by the HealthPartners Data Coordinating Center (DCC); data can be entered via tablets, smart-phones, or computers. After baseline, patient-reported data will be ascertained independent of office visits, and all follow-up patient, OMS and dental assistant data collection will be managed by HP DCC. Follow-up contacts to non-responders will also be managed by the DCC.

- **Overview of Study Schedule**

- The electronic data system used to collect patient and OMS/dental assistant data will be assessed for acceptability and compatibility prior to administration of any questionnaires.
- OMS and their office staff will receive study training from the Study Coordinator (SC), after which the OMS is authorized to begin enrolling study patients.
- An in-office patient log will be kept regarding the reason patients were excluded or declined to participate.
- Once the patient is screened using the *Screening Questionnaire* that comprises the inclusion and exclusion criteria, patients who are eligible will be invited to participate in the study. Potential patients who are interested in study participation will undergo consent procedures.
- Patients will complete these baseline forms and questionnaire before surgery: *Patient Contact and Patient Demographics information*, and *Patient Baseline Questionnaire*.
- Randomization procedures will occur, and patients will receive their randomized assignment.
- The OMS will complete the *Doctor Surgery Questionnaire* after completing the 3rd molar extractions.
- At 1, 3, and 6 months post-baseline, patients will complete follow-up assessments via an online questionnaire. Non-responders will be followed up with email, telephone, and/or texting. All patients will be followed up regardless of whether they report TMD pain at any follow-up.

- Midway through and at the end of the enrollment phase of the study, the OMS and dental assistants will complete a questionnaire regarding their experience with the use of the device.

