## 12 STATISTICAL CONSIDERATIONS

### 12.1 Study Hypotheses

The risk of developing TMD pain in patients undergoing 3rd molars removal in the EC group will be statistically lower within the 6-month follow-up interval than in the UC group.

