### 12.2 Sample Size Considerations

This study's sample size is based on the incidence of TMD pain following 3rd molar removal reported by Huang et al. That observational study reported that among patients undergoing 3rd molar removal, the incidence of jaw joint symptoms lasting more than 1 month was 34.3 per 100 person-years. Among those who did not have a 3rd molar extraction, the rate was 8.8, for a relative risk of 3.8. The incidence of TMD pain reported by patients undergoing surgery was over 30%.

**Primary analysis.** We present a conservative power calculation that assumes we have a single binary outcome (TMD pain yes vs. no) instead of the three measures per person we will collect. The calculations shown below assume two-sided tests and a false positive rate of 5% (alpha = 0.05).

Table 1 shows that 132 patients per group gives 80% power to detect a conservative relative risk of 2.0. To estimate this, we considered a TMD pain incidence of 14% and alpha (type I error) 5%. Table 1's incidences and relative risks are based on data from Huang et al. Note that Huang et al. reported TMD pain incidence over 30%; the current study will have adequate power if the control group's TMD pain incidence is much lower. We will randomize 294 subjects into the study. Assuming 10% loss to follow-up (90% retention), the total sample size will be 264 (132 per group). The assumed retention of 90% is a conservative estimate based on [name] experience in his previous RCT, where 98 of 106 (92%) TMD participants completed their 5-year follow-up visit. Therefore, we anticipate, with patient incentives, that we will obtain 90% or more retention at the 6-month follow-up.

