## 12.4 Final Analysis Plan

All analyses will be by intention-to-treat, with participants included in the group (UC or EC) to which they were randomly assigned.

**Primary analysis.** The primary outcome is incidence of TMD pain within a 6-month follow-up period (a binary dependent variable). The incidence of TMD pain post-surgically will be compared between UC and EC groups. This primary TMD outcome is deemed to have occurred if the patient's self report in the *Patient 1-, 3- and 6-month Follow-up Questionnaires* endorses either or both of the following questions: Pain in jaw with wide opening, or pain in temples, jaw joints or jaw muscles. The primary analysis will include all available follow-up measures (1, 3, and 6 months) for each participant to

estimate incident TMD pain. The UC and EC groups will be compared using an analysis that has the form of logistic regression, but which accounts for correlation of visits within participants using generalized estimating equations (GEE) with each participant being a cluster. The analysis will include group (UC vs. EC), which tests whether the two groups differ in overall frequency of TMD pain; time (1, 3, and 6 months, as a categorical factor); and their interaction (i.e., the time-by-group interaction), which tests for different patterns of change over time in frequency of TMD pain.

In the event of noteworthy amounts of missing data (e.g., patients lost to follow-up or questionnaires not completed), we will check the primary analysis by using standard multiple imputation methods, as implemented in the most recent version of the SAS software (SAS Institute Inc., Cary NC, v. 9.4 or higher), to multiply impute missing data and perform tests. Specifically, we will use SAS's FCS method to create 20 "complete" datasets and otherwise use the defaults in SAS's procedures.

**Secondary analysis.** The primary analysis will not include adjusters, as the randomization should balance the groups. As a check on this, an adjusted version of the primary analysis will include adjusters differing substantially between the two randomized groups, selected from the list of potential adjusters given below (see "Potential Adjusters", below).

Other secondary analyses are as follows:

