1. The incidence of TMD pain, as measured with the validated *TMD Pain Screener Questionnaire* (*binary dependent variable*), will be compared between the UC and EC groups within a 6-month follow-up period based on patients' self report in the *Patient 1-, 3- and 6-month Follow-up Questionnaire*. These analyses will have the same form as the primary analysis.
2. TMD pain intensity, as measured with the validated Characteristic Pain Intensity (CPI) within a 6-month follow-up period (treated as a continuous measure), will be compared between the UC and EC groups based on patients' self report in the *Patient 1-, 3- and 6-month Follow-up Questionnaire*. Unadjusted and adjusted analyses (using adjusters selected as described above) will be performed using GEE as in the primary analysis.
3. Baseline characteristics, specifically all of the potential adjusters listed below (see "Potential Adjusters", below), will be compared between the UC and EC groups. Analyses will use t-tests, possibly after transforming the measure because it has a skewed distribution, Chi-squared test and Fisher's Exact Test.

4. The UC and EC groups will be compared for TMJ noise, pain characteristics (e.g., location in temple or jaw, and occurrence with wide opening of mouth) and change in jaw pain since it started, within a 6-month follow-up period based on patients' self report in the *Patient 1-, 3- and 6-month Follow-up Questionnaire*. These analyses will have the same form as the primary analysis.
5. A descriptive summary of the experiences of surgeons and dental assistants with the new device at mid-way through recruitment of patients and at the end of recruitment based on their self report in the *Doctor Questionnaire Regarding Use of the Device* and *Dental Assistant Questionnaire Regarding Use of the Device*, respectively,

All analyses will use SAS version 9.4 or later (SAS Institute Inc., Cary, NC). All tests will use a significance threshold of 0.05 (2-tailed).

Potential adjusters: The following characteristics will be compared between the UC and EC groups as potential adjusters:

- Patient demographics
- Baseline patient-reported symptoms (e.g., TMJ noise, pain or discomfort around wisdom teeth, frequency of oral habits as measured with the Oral Behaviors Checklist (OBC), and health status; see *Patient Baseline Questionnaire*).

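### The primary GEE tests how often pain is reported across visits, not whether a patient develops TMD pain within 6 months, so the stated 80% power is not assured for the planned test

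*Combined protocol and SAP*

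**What the plan says.** Section 3.2.1 sets the outcome: "The primary outcome is the incidence of TMD pain within a 6-month follow-up period (binary dependent variable". Section 12.1 gives the hypothesis in the same terms: "The risk of developing TMD pain in patients undergoing 3rd molars removal in the EC group will be statistically lower" than in UC. Section 12.2 sizes the trial on that basis: "We present a conservative power calculation that assumes we have a single binary outcome (TMD pain yes vs. no) instead of the three measures" that will be collected. It concludes: "Table 1 shows that 132 patients per group gives 80% power to detect a conservative relative risk of 2.0".

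Section 12.4 restates the outcome and then specifies a logistic model fitted by GEE. The patient is the cluster, every available visit is a record, and the terms are group, categorical time and group-by-time. On the group term: "The analysis will include group (UC vs. EC), which tests whether the two groups differ in overall frequency of TMD pain". No coding, contrast, visit weights or working correlation is given.

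Section 4 adds: "All patients will be followed up regardless of whether they report TMD pain at any follow-up". For the TMD Pain Screener incidence outcome, Section 12.4 says: "These analyses will have the same form as the primary analysis".

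**The concern.** Visit-level frequency is incidence multiplied by persistence. Patients stay in the series after their first report of pain, so later records measure persistence or recurrence, and one case can count once, twice or three times. The stated hypothesis is about developing pain, and no analysis in the plan tests that directly.

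The deciding test is also not fixed. With group-by-time in the model, the group coefficient is the effect at one visit under reference coding and an average over visits under effect coding.

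Two wrong conclusions become possible. A device that halves the number of patients who develop pain can fail if the pain it prevents is mostly short-lived. A device that leaves incidence unchanged but shortens episodes can be reported as reducing incidence.

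**Working it through.** **1. The plan's own figure.** Inputs from Section 12.2: two-sided alpha 0.05, 80% power, incidence 14%, relative risk 2.0. The pooled-variance formula is

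n = [1.96·√(2p̄(1−p̄)) + 0.8416·√(p₁(1−p₁) + p₂(1−p₂))]² / (p₁−p₂)².

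With p₁ = 0.28, p₂ = 0.14, p̄ = 0.21: (1.96 × 0.5760 + 0.8416 × 0.5675)² / 0.0196 = 2.581 / 0.0196 = 131.7, so 132 per group. All 12 cells of Table 1 reproduce within 0.5 patient if the row is the EC incidence and UC is that figure times the relative risk. Taking 14% v 7% instead would need 300 per group. So 28% v 14% is inferred, and it is a comparison of one yes/no per patient. Also 294 × 0.9 = 264.6, which matches the stated 264.

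**2. The planned test at the same incidences.** The documents give no visit-level rates, so the patterns of pain at months 1/3/6 among cases (1 = pain) are my assumptions:

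- All visits: 111.
- One random visit: 100, 010, 001, one third each.
- Mixed: 100 40%, 010 10%, 001 10%, 110 15%, 101 2%, 011 3%, 111 20%.
- Mostly month 1: 100 70%, 010 5%, 001 5%, 110 10%, 111 10%.
- Transient pain mainly prevented: UC 14% of patients 100 and 14% 111; EC 2% and 12%.
- Persistent pain mainly prevented: same UC; EC 11.2% 100 and 2.8% 111.
- Equal incidence: 28% in both arms; cases are 40% 100 and 60% 111 in UC, 80% and 20% in EC.

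Two readings of the overall group test are used: the equal-weight mean of the three visit log odds ratios (averaged), and the log odds ratio of the mean visit frequency (pooled). The variance is g′Cg/n per arm, where C is the covariance of the three visit responses and g is the gradient of the contrast.

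*Transient pain mainly prevented, by hand.* Visit rates are UC 28/14/14% and EC 14/12/12%. Log odds ratios are 0.871, 0.177, 0.177; mean 0.408, SE 0.335, z = 1.22. Power ≈ Φ(1.22 − 1.96) = 23%.

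*Equal incidence, by hand.* Visit rates are UC 28/16.8/16.8% and EC 28/5.6/5.6%. Log odds ratios are 0, 1.225, 1.225; mean 0.817, SE 0.351, z = 2.33. Rejection ≈ Φ(2.33 − 1.96) = 64%.

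**3. Simulation** (4000 trials per scenario, 132 per arm, no missed visits):

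| Scenario | Any-visit test | GEE averaged | GEE pooled |
|---|---|---|---|
| 28% v 14%, pain at all visits | 80–82% | 80% | 80% |
| 28% v 14%, one random visit | 80–82% | 79% | 80% |
| 28% v 14%, mixed | 80–82% | 63% | 68% |
| 28% v 14%, mostly month 1 | 80–82% | 41% | 68% |
| 28% v 14%, transient mainly prevented | 80–82% | 22% | 28% |
| 28% v 14%, persistent mainly prevented | 80–82% | 95% | 96% |
| 28% v 28%, shorter EC episodes | 5% | 67% | 50% |

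The any-visit column gives the range over all six 28% v 14% rows. The 41% falls to 37% if trials with an empty visit cell are excluded.

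**4. Coding alone.** In the transient scenario, the group coefficient has 79% power with month 1 as the reference visit and 7% with month 6.

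**5. A second model.** Correlated latent-normal visits, with cumulative incidence held at 28% v 14%, give the averaged contrast 56–83% power when persistence is equal in the two arms (pooled 75–84%). They give 23–29% when EC cases are fewer but more persistent.

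**6. Missed visits.** Assume 147 randomized per arm, 10% lost and a further 10% of visits missed at random (600 trials per scenario, Monte Carlo SE about 2 points). The any-visit test after FCS imputation with 20 datasets has 71–77% power across the 28% v 14% scenarios and rejects 4% under the null. The GEE (averaged/pooled) has 77/77% with pain at all visits, 60/66% mixed and 38/63% mostly month 1.

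**The case against.** The plan says openly, in Sections 3.2.1 and 12.4, that all three follow-up measures enter the primary analysis, and it never says the outcome is pain at any visit. On that view the sponsor chose a repeated-measures analysis and used the word incidence loosely. The power text can also be read as one measure at 28% v 14%, with further measures adding information. If those rates held at every visit, the averaged contrast would have 86–99% power and the label 'conservative' would be right.

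The most striking figures, 22/28% and 67/50%, need the device to change episode length separately from onset, which no section supports. With equal persistence and flat visit rates the GEE has 81–84% in the latent-normal model. The 41% is partly sparse-cell behaviour. The preferred fix does not restore 80% either once visits are missed.

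The size of any loss does depend on these assumptions. The mismatch does not. The per-visit reading implies a cumulative incidence of about 34–58% v 18–34%, which is a different quantity from the one the outcome and hypothesis describe. Stating the intent as overall frequency does not fix visit weights when an interaction is in the model. The recall period of the questions is not given, so a record may mean pain at the visit or over an interval; the mismatch holds either way.

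**Conclusion.** The concern holds. The primary p-value need not test the stated hypothesis, and the 80% power belongs to a patient-level comparison that the plan never makes. At 28% v 14% with complete data, the any-visit test keeps 80–82% power whatever the persistence. The planned test ranges from 22% to 96% over the patterns tabulated, and can reject in half to two thirds of trials when incidence is equal. These figures are illustrative: they rest on assumed persistence patterns and on 28% v 14% as the cumulative incidences behind Table 1. Power is near 80% when pain is present at all visits or at one random visit. Because this is the trial's single primary test, it must be fixed before outcome data are analysed.

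**What to change.** **Preferred.** Make the primary analysis one record per patient: any endorsement at 1, 3 or 6 months, yes or no, compared by risk ratio and risk difference with one group test. An observed endorsement makes the patient a case. Otherwise, impute missed visits with the FCS method already named in Section 12.4, with group and all three visit responses in the imputation model, before forming the indicator. Patients with partial follow-up are then not scored pain-free by default. Keep the GEE as a secondary analysis of visit-level frequency, with its overall contrast named. Make the same change for the TMD Pain Screener incidence analysis. In Section 12.2, remove 'conservative' and state power allowing for missed visits.

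**Alternative.** If visit-level frequency is what the sponsor wants as primary, say so in the outcome and hypothesis, name how visits are averaged, and restate power for that contrast under stated persistence assumptions.

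**Cost.** SAP wording and a short program; no new data. Under the preferred route, imputation moves from a check into the primary analysis, power is about 71–77% rather than 80% if visits are missed as assumed above, and the time pattern becomes secondary.

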## 5 STUDY ENROLLMENT AND WITHDRAWAL

The target sample size for this study is 294 patients. To meet this target, we anticipate that 500 patients will need to be screened. Enrollment will include patients who present to the participating oral & maxillofacial clinics for surgical removal of mandibular bilateral 3rd molars (concurrent removal of maxillary 3rd molars is allowed). Each OMS will enroll no more than 60 patients into the trial.

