### **5.4 Treatment Assignment Procedures**

The specific randomization procedure and methods are described below. Generally, participants will be randomized between the two study treatments, stratified by surgeon (7 surgeons and thus 7 strata total). This stratification addresses variation between surgeons in surgical technique and variation between practices in postoperative rehabilitation protocol.

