#### **5.4.1 Randomization Procedures**

The OMS or dental assistant will provide a participant with the randomization assignment after the participant's eligibility is confirmed and his/her consent is obtained. The random assignment will be obtained from the study tablet used by the OMS or dental assistant. The study tablet, which will be programmed by the HP DCC, will (among other things) use randomized treatment assignments from a stratum-specific

(i.e., surgeon-specific) sequence of randomized assignments created as described in the following paragraph. Each surgeon-specific randomization sequence will be loaded into the tablet by the programmer at the HP DCC in such a way that it will be impossible for clinical study personnel, in particular for the OMS or dental assistant to access this sequence or to infer any treatment assignment in the sequence until the moment that assignment is given to a particular participant.

For each stratum (i.e., surgeon), the randomization sequence will be created by the project statistician using custom-written code in the R system (R Foundation for Statistical Computing, Vienna, Austria, <https://www.R-project.org/>), as follows: The sequence will use randomized permuted blocks of size 2 and 4, in each of which the two treatments are present equally often. The R code will first generate a random sequence of block lengths, so that study personnel will never be able to tell which block they are in, and then in each block, the treatment assignments will be randomly permuted, so that each sequence of possible treatments within a block is equally probable.

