#### **5.5.2 *Handling of Subject Withdrawals or Subject Discontinuation of Study Intervention***

All patients who provide consent and are randomized to one of the treatment arms will continue to provide data unless and until they explicitly withdraw their consent for further data collection. Only participants who no longer consent to provide data will be excluded from further data collection, and data collected during the duration of their participation will be included.

For patients who cease to receive their assigned treatment or who withdraw from study participation, the date and reason for this change in status will be recorded. Patients who have withdrawn consent for study participation may continue to receive usual care as patients of the participating OMS.

OMS will not replace patients who have withdrawn from the study; the study's sample size was chosen to account for 10% of patients not providing follow-up data.

If any OMS or DA withdraws from study participation, he/she will be replaced, and the replacement(s) will be trained on study procedures prior to participating in the trial.

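### Randomization is stratified by surgeon but the primary GEE and its sister models omit surgeon; if pain rates differ by surgeon, the test is mildly conservative and forgoes about 0 to 3 power points

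*Combined protocol and SAP*

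**What the plan says.** **Design.** Section 5.4 states that "participants will be randomized between the two study treatments, stratified by surgeon (7 surgeons and thus 7 strata total"). The reason given is that "This stratification addresses variation between surgeons in surgical technique and variation between practices in postoperative rehabilitation protocol". Section 5.4.1 adds that "The sequence will use randomized permuted blocks of size 2 and 4, in each of which the two treatments are present equally often", with a separate sequence for each surgeon.

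**Primary analysis.** The model in Section 12.4 is a logistic GEE with the participant as cluster and with terms for group, categorical time and their interaction. No covariates enter: "The primary analysis will not include adjusters, as the randomization should balance the groups".

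**Secondary analyses.** For the TMD pain screener, and for TMJ noise, pain characteristics and change in jaw pain, Section 12.4 says "These analyses will have the same form as the primary analysis". Pain intensity (CPI) is also analysed by GEE as in the primary analysis, without and with adjusters.

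**Adjusted check.** It uses "adjusters differing substantially between the two randomized groups, selected from the list of potential adjusters given below". The list covers demographics, baseline symptoms, the surgeon's clinical findings and procedural characteristics. Neither surgeon nor site is on it.

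**The concern.** The design spends effort on balancing the arms within surgeon, and the analysis does not use that balance. Nothing else in the plan fills the gap. Surgeon is not a candidate adjuster, and the selection rule looks for imbalance between arms, which blocking within surgeon is meant to prevent. The adjusted check is therefore unlikely ever to include the stratification factor.

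The stated reason for having no adjusters supports the absence of bias. It does not address the standard error. When strata differ in outcome, forced balance removes the between-stratum part of the variance from the treatment contrast, but an unadjusted standard error still includes it. The test then rejects less often than 5% under the null and gives up some power. All of this depends on pain rates differing by surgeon. Section 5.4 speaks of technique and rehabilitation, not of TMD pain rates.

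**Working it through.** **1. The plan's own figure.** Section 12.2 gives 132 per group for 80% power, 14% incidence, relative risk 2.0 and two-sided alpha 0.05. With 14% vs 28% (mean 21%), pooled variance and no continuity correction:

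n = [1.960·√(2·0.21·0.79) + 0.842·√(0.28·0.72 + 0.14·0.86)]² / 0.14² = [1.960·0.5760 + 0.842·0.5675]² / 0.0196 = 131.7, so 132.

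This agrees. Allowing for 10% loss, 264/0.9 = 293.3, so 294 after rounding up to a whole patient.

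**2. Mechanism.** Let p_s be the pain risk for surgeon s and p̄ its mean. Then p̄(1−p̄) = mean of p_s(1−p_s) + variance of p_s. The unadjusted standard error uses the left side. With arms balanced within surgeon, the difference between arms varies only with the first term on the right.

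**3. Simulation, single binary outcome.** The setting is seven surgeons with 19 patients per arm each (133 per arm), normal surgeon effects on the logit scale, and marginal risks held at 28%/28% for type I error and 28%/14% for power. There were 40,000 trials per setting. The comparison is the two-proportion test against Cochran-Mantel-Haenszel by surgeon. The surgeon SD is an assumption, because the documents give none.

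| Surgeon SD (logit) | Control risk at ±1 SD | Type I error, unadjusted vs stratified | Power, unadjusted vs stratified |
|---|---|---|---|
| 0 | 28% | 5.1 vs 5.1% | 81.4 vs 81.2% |
| 0.3 | 22 to 34% | 4.8 vs 4.9% | 81.0 vs 81.1% |
| 0.5 | 18 to 38% | 4.6 vs 5.0% | 81.1 vs 82.0% |
| 0.8 | 13 to 43% | 4.2 vs 5.1% | 81.6 vs 83.6% |
| 1.0 | 11 to 47% | 3.6 vs 5.0% | 82.1 vs 84.9% |

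**4. Hand check from the standard errors.** In the same runs the SE of the risk difference, unadjusted vs stratified, was 0.0488 vs 0.0481 at SD 0.5 and 0.0483 vs 0.0455 at SD 1.0.

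- Level: the effective critical value is 1.960 × (0.0488/0.0481) = 1.988, a level of 4.7%. At SD 1.0 it is 1.960 × (0.0483/0.0455) = 2.081, a level of 3.7%.
- Power at SD 0.5: Φ[(0.14 − 1.960·0.0488)/0.0481] = Φ(0.922) = 82.2% unadjusted, and Φ(0.14/0.0481 − 1.960) = Φ(0.951) = 82.9% stratified. The gain is 0.7 points.
- Power at SD 1.0: Φ(0.996) = 84.0% and Φ(1.117) = 86.8%. The gain is 2.8 points.

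Absolute power is slightly higher than simulated because these are unpooled standard errors. The levels and gains match. A separate normal approximation at 132 per group gives gains of 0.0, 0.9 and 3.2 points at SD 0, 0.5 and 1.0, and an unadjusted level of 5.0, 4.6 and 3.7% at a common rate of 21%.

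**5. Unequal enrollment.** Section 5 says "Each OMS will enroll no more than 60 patients into the trial". If four surgeons reach 60, the other three share 294 − 240 = 54, or 18 each. After 10% loss that is about 27 and 8 per arm. Power is then 80.7 vs 81.4% at SD 0.5 and 81.4 vs 84.2% at SD 1.0.

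**6. The planned three-visit GEE.** The gain depends on how pain recurs across visits, which the documents do not give. Two assumptions were tried.

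- *A patient with pain reports it at each visit with probability 0.6, at least once* (about 4,000 trials per setting). Type I error without vs with surgeon is 4.5 vs 5.2% at SD 0.5 and 3.9 vs 5.1% at SD 1.0. Power rises by 1.7 and 4.3 points, but about 1.0 point of rise also appears at SD 0 (small-sample robust SE). That leaves roughly 0.6 to 0.7 and 3.3.
- *28% vs 14% at every visit, patient random-effect SD 2* (8,000 trials per setting). The unadjusted level is 5.0, 4.6 and 4.3% at SD 0, 0.5 and 1.0. The gain is only 0.1, 0.2 and 0.8 points, because power is already about 96%.

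In the first of these the SE of the log odds ratio does not shrink (0.326 to 0.329 at SD 0.5; 0.335 to 0.340 at SD 1.0). The gain comes from the odds ratio becoming surgeon-conditional (0.435 to 0.423; 0.430 to 0.402).

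**7. Sparse strata.** With equal enrollment at least one surgeon has no events in 2% of trials at SD 0.5 and 21% at SD 1.0. With the unequal enrollment of step 5 this becomes 14% and 38%.

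**The case against.** The case for leaving the plan alone is a fair one. Using no adjusters is an explicit, prespecified choice, and the resulting test is valid and at worst slightly conservative. The between-surgeon SD is assumed. At SD 1.0 the control rates would run from about 7% to 59% across seven surgeons, so 3 points is generous and 0 to 1 is the more likely gain. The headline range comes from the single-outcome test rather than the planned GEE, where the gain may be negligible.

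Adjustment also has costs. It moves the odds ratio from marginal to surgeon-conditional. With uncorrected robust standard errors the adjusted logistic models showed type I error of 5.0 to 5.6% in the runs above, and 4.3 to 6.4% in a smaller run of 2,500 trials per setting. Zero-event surgeons would be commoner if risks were lower: at 14% vs 7%, in 27% of trials at SD 0.5 and 64% at SD 1.0 with equal enrollment.

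All of this stands, and it limits the weight of the point. It does not remove the mismatch between design and analysis. The mild conservatism appears in every set of runs once surgeons differ clearly (SD 0.5 and above). The sparse-stratum and small-sample difficulties are reasons to write the rules in advance. The Mantel-Haenszel test by surgeon held its level (4.9 to 5.1%) throughout.

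**Conclusion.** The point holds as one of efficiency, not validity. The primary GEE and the secondary models of the same form omit the randomization stratum, and the adjusted check is unlikely to bring it in. There is no bias or inflated type I error, and 132 per group still gives about 80% power on the sizing outcome.

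For assumed surgeon SDs of 0 to 1.0 on the logit scale and risks of 28% vs 14%, the unadjusted test runs at about 5.1% down to 3.6% and forgoes about 0 to 3 power points. The loss is 0 to 1 at SD 0.3 to 0.5 and nil if surgeons do not differ. For the three-visit GEE the direction is the same, but the size depends on the assumed visit pattern: from below 1 point to about 3.3 at SD 1.0.

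**What to change.** Before unblinding, amend Section 12.4 as follows:

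- Include surgeon, as randomized, in the primary model and in the secondary models of the same form. Adding it later would be a post hoc model choice.
- State whether the reported effect is surgeon-conditional or marginal. To keep it marginal, report a standardized risk difference and risk ratio from the surgeon-adjusted model, with a variance that reflects the adjustment. Alternatively, use a surgeon-stratified Mantel-Haenszel risk difference and risk ratio for the per-patient outcome.
- Treat a replacement surgeon as a separate stratum, since Section 5.5.2 provides that "If any OMS or DA withdraws from study participation, he/she will be replaced".
- Fix a rule for pooling sparse strata within practice, and name the small-sample treatment of the robust standard error.

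**Cost.** The change needs a short SAP edit and six extra model parameters (seven surgeons less one), with no new data. It does require a decision on the estimand: the conditional odds ratio differs from the planned marginal one, and the Mantel-Haenszel option targets a different quantity from the planned GEE.
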